### 3.2.3 Analysis periods

The start and end dates of each study period are used for the classification of seizure data and TEAEs for applicable summaries. The exact start and end of each of these periods is described for calculation purposes in [Table 3–3.21](#). Measurements from diaries returned on the start date of a subsequent period would be included in calculations for the previous period.

**Table 3–3.21: Start and end of EP0093 analysis periods**

Description	Start	End	Details
Evaluation Period	Entry Visit (EV, Visit 1)	EOS or EDV or the last contact date if neither EOS or EDV visit is available.  At the time of a clinical cutoff prior to the study completion, if a subject is ongoing and doesn't have the EDV, the end of the period is set to the clinical cutoff date.	The Entry Visit (EV, Visit 1) will be done on the same day as the last visit of the parent study. Subjects will return to clinic every 2 weeks during Month 1, every month during Month 2-3, every 3 months after Month 3 up to Month 24.
Taper Period/ Safety Follow-Up Period	1 day after end date of evaluation period.	The date of final contact.  At the time of a clinical cutoff prior to the study completion, if a subject is ongoing, the end of the period is set to the clinical cutoff date.	Applies only to patients who discontinue the study or complete it without continuation of PSL treatment.
Exposure Period	Date of first dose of PSL	Date of last dose of PSL	Extends from the date of first dose until the last dose of PSL in EP0093. It may include the Evaluation and Taper Period. (Section 3.2.2.1).

At the time of a clinical cutoff prior to the study completion, subjects without the Study Termination eCRF will be classified as “ongoing.” Only the data on or prior to the clinical cutoff date will be included in the analyses.

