- ^g Full physical examination will include assessment of cardiac and respiratory function via auscultation and review of the following body systems: general appearance; ear, nose, and throat; eyes; hair and skin; respiratory; cardiovascular; gastrointestinal; musculoskeletal; hepatic; neurological; and mental status. Brief physical examinations will include a review of the following body systems: general appearance (including mental status); skin; respiratory; cardiovascular; gastrointestinal; and hepatic.
- ^h Brief neurological examination will include a general assessment and evaluation of reflexes, muscle strength and coordination and cerebellar function. Full neurological examination will include in addition, evaluation of cranial nerves, motor system (general muscle strength and tone), and sensations in upper/lower extremities.
- ⁱ Personal outcome assessments will be completed at Visit 6 (Month 6) and Visit 11 (Month 21) (for subjects who agree to participate).
- ^j An ECG at the SFU will be performed only if abnormal at the EOS or EDV Visit. All ECG recordings will be performed with the subject resting in supine position for at least 5 minutes.
- ^k Only subjects who do not require tapering of PSL at M24 will have an echocardiogram at M24. All other subjects will have an echocardiogram at the SFU Visit and at 6 months after the last dose of PSL. A repeat echocardiogram will be performed for subjects with a new finding, Grade 2 severity (moderate), or Grade 3 severity (severe) (see [Section 6.3](#)).
- ^l Results of a serum pregnancy test performed during parent study will be used at Visit 1 together with a urine test performed at Visit 1. Urine pregnancy tests will be used at all other visits for female subjects of childbearing potential.
- ^m Seizure counts are collected on the subject's daily record card on a daily basis.
- ⁿ Assessment includes AED history.
- ^o Medication should be presented at each visit for check on compliance.
- ^p PSL will be dispensed at the EOS Visit only to subjects who will be tapered off PSL.
- ^q The study termination assessment at the EOS visit is for subjects who will transfer into either a Managed Access Program or another PSL study.
- ^r The study termination assessment at the SFU Visit is for subjects who withdraw early or who complete the study, but will not be transferred to either a Managed Access Program or another PSL study.

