Evaluation of PDILI must be initiated as described in [Section 9.2.1](#). If subjects are unable to comply with the applicable monitoring schedule, PSL must be discontinued immediately. Investigators should attempt to obtain information on subjects in the case of PSL discontinuation to complete the final evaluation. Subjects with PDILI should not be withdrawn from the study until investigation and monitoring are complete. All results of these evaluations and observations, as well as the reason(s) for PSL discontinuation and subject withdrawal (if applicable), must be recorded in the source documents. The eCRF must document the primary reason for PSL discontinuation.

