- r The study termination assessment at the SFU Visit is for subjects who withdraw early or who complete the study, but will not be transferred to either a Managed Access Program or another PSL study.

**Error! Reference source not found.** Data may be collected through phone or video calls for visits that do not require onsite assessment because of COVID-19 pandemic.

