### **3.2.2 Analysis time points**

#### **3.2.2.1 First and last dose of PSL**

Unless otherwise noted, all references to the first dose of PSL in this SAP refer to the first dose of PSL during EP0093 (i.e. not the first dose of PSL from the parent studies in which subjects participated in prior to EP0093).

At the time of a clinical cutoff, for subjects who are ongoing and don't have the End of Taper Visit, the last dose of PSL will be set to the date of the clinical cutoff for the interim analyses. For subjects who are ongoing but had the End of Taper Visit at the time of a clinical cutoff, the last dose of PSL will be set to the last dosing date on the Study Medication Administration eCRF for the interim analyses.

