#### **3.2.2.3 Study Entry visit**

#### **3.2.2.4 The Entry Visit (EV, Visit 1) will be done on the same day as the last visit of the parent study. End date of the Evaluation Period**

The end date of the Evaluation Period will be either EOS at Month 24 or EDV for subjects who discontinue early. If a subject does not have an EOS or EDV Visit, then the final contact date will define the end date of the Evaluation Period. At the time of a clinical cutoff prior to the study completion, if a subject is ongoing and doesn't have the EDV, the end of the Evaluation Period is set to the clinical cutoff date.

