### 10.2.2.11 Time to Discontinuation to Treatment

Kaplan-Meier estimates of the percentage of subjects completing 3, 6, 12, 18, and 24 months of treatment will be provided for the SS. For subjects who discontinued from the study, the event date is set to the date of last dose of PSL and the time to event will be calculated as the date of

last dose minus the date of first dose of PSL in EP0093 plus 1. Subjects who completed the study will be censored as of the date of last dose of PSL in EP0093. At a clinical cutoff, subjects who are ongoing will be censored as of the date of last dose of PSL defined for the interim analyses (Section 3.2.2.1).

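### At a clinical cutoff, subjects who have withdrawn and taken their last dose are censored until the Study Termination form exists, so Kaplan-Meier retention in pre-completion reports is slightly too high

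*SAP*

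**What the plan says.** Four SAP rules act together when data are reported at a clinical cutoff.

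- **Status (3.2.3, table of analysis periods).** "At the time of a clinical cutoff prior to the study completion, subjects without the Study Termination eCRF will be classified as" ongoing. Dosing status and a completed EDV play no part.
- **Retention (10.2.2.11).** At a cutoff, "subjects who are ongoing will be censored as of the date of last dose of PSL", using the last dose defined in 3.2.2.1. Only subjects who discontinued from the study are events, dated at last dose. Estimates are planned at 3, 6, 12, 18 and 24 months.
- **Last dose (3.2.2.1).** For ongoing subjects without "the End of Taper Visit, the last dose of PSL will be set to the date of the clinical cutoff for the interim analyses". Once the End of Taper Visit has taken place, the recorded last dosing date is used.
- **Evaluation Period (3.2.2.4).** If a subject is ongoing and has no EDV, "the end of the Evaluation Period is set to the clinical cutoff date".

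The timing of the form comes from footnote r of the schedule of assessments, the same in both documents: "The study termination assessment at the SFU Visit is for subjects who withdraw early or who complete the study" without transferring to another source of PSL. Protocol 8.3.1 places the SFU Visit 30 days after last intake, plus or minus 1 week.

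**The concern.** A subject can have had an EDV, finished the taper and have a recorded last dose, and still be ongoing because the form is not yet due. SAP 3.2.2.1 foresees this case, since it gives ongoing subjects who are past the End of Taper Visit their true last dosing date. SAP 10.2.2.11 then censors them on that date. The plan thus censors known stoppers at the moment they stop. That censoring is informative and acts in one direction only, towards higher retention.

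The last-dose rule adds a smaller error. A subject off PSL but without an End of Taper Visit is treated as dosed up to the cutoff. This feeds exposure duration (SAP 9.1) and the Exposure Period used for safety intervals and for last, minimum and maximum values (SAP 3.2.4, 3.2.5).

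Protocol 12.7 and SAP 4.2 allow data to be reported before completion in annual reports, regulatory submissions and publications. The cutoff rules serve that use.

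**Working it through.** The plan gives no retention figure to reproduce. The windows below come from the documents. Accrual, discontinuation rates and cutoff dates are assumptions.

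**Length of the gaps**
- Last dose to Study Termination form: 30 days, or 23 to 37 with the window.
- Last dose to End of Taper Visit: 7 days, or 0 to 14 with the 1-week window in Protocol 8.2.1.

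**Hand example.** 100 subjects enter together. Ten have last dose on day 40 and their form by day 70. Ten more have last dose on day 80, with the form due on day 110. The cutoff is day 100.
- By actual last dose, retention at day 90 is (1 − 10/100) × (1 − 10/90) = 80%.
- Under the SAP rule the second ten are censored, so it is 1 − 10/100 = 90%.

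**Staggered entry.** Let λ be the daily hazard of stopping and P(t) the proportion of subjects whose potential follow-up at the cutoff is at least t days. A stop on day t counts only if follow-up reaches t + 30, so the recorded hazard is λ × P(t+30)/P(t). The cumulative hazard lost by day T is D(T) = λ∫[1 − P(t+30)/P(t)]dt over 0 to T. The overstatement is S(T) × (e^D − 1), with S(T) = e^(−λT). Accrual is uniform over 365 days and a month is 30 days, as in SAP 3.2.5.

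Monthly rates of 2% and 5% give λ = −ln(0.98)/30 = 0.000673 and −ln(0.95)/30 = 0.00171.

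*Cutoff at 12 months (day 365).* P(t) = (365 − t)/365, so the integrand is 30/(365 − t) and D(180) = 30λ × ln(365/185) = 20.4λ.
- 2%: D = 0.0137, S = 0.886, overstatement 0.886 × 0.0138 = 1.2 points.
- 5%: D = 0.0349, S = 0.735, overstatement 0.735 × 0.0355 = 2.6 points.

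*Cutoff at 18 months (day 547.5).* P(t) = 1 up to day 182.5, then (547.5 − t)/365. No stop is lost before day 152.5, so the 3-month estimate is unaffected.
- 6 months: D(180) = λ × 27.5²/(2 × 365) = 1.04λ, giving 0.06 to 0.13 point.
- 12 months: D(360) = λ × [30²/(2 × 365) + 30 × ln(365/187.5)] = 21.2λ. At 2%, 0.785 × 0.0144 = 1.1 points. At 5%, 0.540 × 0.0369 = 2.0 points.

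A simulation with the lag spread evenly over 23 to 37 days, and with the End of Taper rule applied, gives the same values to one decimal.

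**Other assumptions.** For 1000 subjects, 365-day accrual, a cutoff 120 days later and 20%, 40% or 60% discontinuation by 12 months, simulated 12-month retention is:

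| Assumed discontinuation | SAP rule | Actual last dose | Difference |
|---|---|---|---|
| 20% | 81.5% | 80.0% | 1.5 |
| 40% | 62.8% | 59.9% | 2.9 |
| 60% | 43.7% | 40.2% | 3.5 |

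About 15 to 38 subjects have stopped but are censored. About 3 to 9 of them are credited with dosing to the cutoff, for roughly 10 to 27 extra days in total.

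**The case against.** The strongest reply concerns scope. The SAP is written to support the final study report, no formal interim analysis is planned, and early reporting is only permitted. At the end of the study each subject should have a termination form and the cutoff rules fall away. Nothing is tested. All of this stands, and it keeps the point minor.

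Four stronger readings are tempting, and the documents do not support them.

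- **The primary efficacy variable is contaminated by taper or off-drug diary days.** Subjects with an EDV are expressly outside the Evaluation Period extension. The cutoff sentence omits End of Study (EOS), but the rule just before it ends the period at EOS or EDV, so this is mainly a drafting gap. EOS is at Month 24, so nobody reaches it in the scenarios above.
- **Subjects taken off PSL for potential liver injury (PDILI) are miscounted as retained.** Protocol 6.3.1 says "Subjects with PDILI should not be withdrawn from the study until investigation and monitoring are complete", and 9.2.1.2.1 leaves restart possible in rare cases. The SAP event is discontinuation from the study, so these subjects are not clearly events. What is missing is a stated rule.
- **Exposure is materially inflated.** Protocol 8.2.1 lists the End of Taper Visit for discontinuing subjects in general. When it takes place on time, the excess is about a week per affected subject.
- **Retention is overstated by up to 4.5 points.** A range of 2.3 to 4.5 points arises at 9 months for a 12-month cutoff. The SAP does not report 9 months, and only (365 − 270)/365 = 26% of subjects would have that much follow-up.

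**Conclusion.** The point holds for time to discontinuation in any report made at a clinical cutoff. Basing status only on the termination form censors withdrawn subjects for about 23 to 37 days after their last dose and biases retention upward.

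At time points the SAP reports, with uniform 12-month accrual and 2% to 5% discontinuation per month, the bias is about 1.2 to 2.6 points at 6 months for a 12-month cutoff. For an 18-month cutoff it is about 0.1 point at 6 months and 1.1 to 2.0 points at 12 months. Heavier discontinuation, or many subjects stopping together shortly before a cutoff, would enlarge it. The documents give no rate, accrual pattern or cutoff date, so these figures are illustrations.

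The exposure error is secondary: about a week per affected subject when the End of Taper Visit is on time, and longer if it never takes place. A reader might infer that the final analysis is biased too, but it is not affected. Severity: minor.

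**What to change.** Amend three places in the SAP.

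1. **10.2.2.11.** At a cutoff, count as an event any subject with an EDV or a recorded early discontinuation whose recorded last dose is on or before the cutoff. Date the event at that dose, whether or not the Study Termination form exists. State explicitly how subjects whose PSL is interrupted but who remain on study are handled.
2. **3.2.2.1.** Use the recorded last dosing date whenever permanent cessation is recorded on or before the cutoff. Impute the cutoff date only for subjects still taking PSL then. This includes subjects who have had an EDV and are still tapering, because they have no final dose date yet.
3. **3.2.2.4 and the 3.2.3 table.** Apply the cutoff date only to ongoing subjects who have had neither EOS nor EDV, to match the rule that precedes it.

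The cost is a few sentences and the matching programming. Visit dates and last dosing dates are already collected, so no new data are needed.

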#### 3.2.3.1 Mapping of assessments performed at early discontinuation

Unlike other scheduled visits, an early discontinuation visit (EDV) doesn't have a predetermined visit window and can occur at any days during the study. If an EDV occurs at the day of a scheduled visit, in-clinic safety assessments such as vital signs, ECGs, and blood collection for clinical laboratory assessments, should correspond to that scheduled visit. In-clinic safety assessments at an EDV that occurs on a day between two scheduled visits will be assigned to the next scheduled clinic visit. All other efficacy assessments and questionnaire collected on an EDV will not be mapped.

In the by-visit summary tables, only nominal (scheduled) visits where the assessment is scheduled will be included. Unscheduled visits will not be mapped to scheduled visits. In the subject listing, data will be presented under the actual visits, including EDV and unscheduled visits.

Seizure data collected by diary are associated with periods defined within the study and as such there is no need to map them to visits. If a subject withdraws between visits an effort is made to recover all diary records for use in calculation of seizure frequencies.

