8.1.5 Visit 5 (Month 3 ±1 week)

The following procedures will be performed:

- Verify withdrawal criteria
- Obtain C-SSRS data since the last visit
- Obtain SSG data
- Measure vital signs (pulse rate, systolic BP, diastolic BP, and respiratory rate), in supine position after 5 minutes of rest
- Measure body weight
- Perform brief physical examination (refer to [Section 9.3.4](#) for details)
- Perform brief neurological examination (refer to [Section 9.3.5](#) for details)
- Perform Psychiatric and Mental Status assessment
- Obtain 12-lead ECG
- Obtain echocardiogram

- Collect blood and urine samples for clinical laboratory analyses
- Perform urine pregnancy test (female subjects only)
- Seizure evaluation (count and type) from subject's daily record card
- Record concomitant medication and procedures
- Record AEs
- Record health-related outcomes and HRU (refer to [Section 10.5](#) for details), with the exception of socio-professional status
- Dispense PSL
- Check PSL accountability

8.1.6 Visit 6 (Month 6), Visit 7 (Month 9), Visit 8 (Month 12), Visit 9 (Month 15), Visit 10 (Month 18), and Visit 11 (Month 21) ±1 month

The following procedures will be performed:

- Verify withdrawal criteria
- Obtain C-SSRS data since the last visit
- Obtain HADS data
- Obtain SSG data
- Obtain QOLIE-31-P data (Visit 6, Visit 8, and Visit 10 only)
- Perform Personal Outcomes assessment (Visit 6 and Visit 11 only)
- Measure vital signs (pulse rate, systolic BP, diastolic BP, and respiratory rate), in supine position after 5 minutes of rest
- Measure body weight
- Perform brief physical examination (refer to [Section 9.3.4](#) for details)
- Perform brief neurological examination (refer to [Section 9.3.5](#) for details)
- Perform Psychiatric and Mental Status assessment
- Obtain 12-lead ECG (Visit 7, Visit 9, and Visit 11 only)
- Obtain echocardiogram
- Collect blood and urine samples for clinical laboratory analyses
- Perform urine pregnancy test (female subjects of childbearing potential only)
- Seizure evaluation (count and type) from subject's daily record card
- Record concomitant medication and procedures
- Record AEs
- Record health-related outcomes and HRU (refer to [Section 10.5](#) for details), with the exception of socio-professional status

- Dispense PSL
- Check PSL accountability

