### 9.5.2 Electrocardiograms

The following ECG parameters will be recorded: heart rate, PR-interval, QRS-duration, QT-interval, QTcB [QT corrected for heart rate using Bazett's formula] or QTcF [QT corrected for heart rate using Fridericia's formula], and Investigator's conclusion on ECG profile.

The 12-Lead ECG results are collected at Entry Visit, Visit 3, Visit 5 and at visits every 6 months thereafter. An ECG at the SFU will be performed only if abnormal at EOS or EDV Visit.

For each ECG, the overall ECG result, is also collected, categorized by the investigator as one of: no abnormality, an abnormal but not clinically significant finding, or a clinically significant finding.

QTcB and QTcF will also be presented by following classification per visit:

- Observed results:  $<450\text{ms}$ ,  $450-<480\text{ms}$ ,  $480-<500\text{ms}$  and  $\geq 500\text{ms}$
- Change from Baseline:  $<30\text{ms}$ ,  $30-<60\text{ms}$ ,  $\geq 60\text{ms}$

The observed ECG parameter values and their absolute change from Baseline will be summarized (SS) descriptively for each scheduled assessment visit, as well as Last Visit, maximum value, and minimal value.

The number and percentage of subjects with no abnormality, an abnormal but not clinically significant finding, and a clinically significant finding will be summarized for each of the scheduled assessment visits. Percentages for the visit will be relative to the number of subjects with an ECG result for the visit.

The number and percentage of subjects with an abnormal ECG value described in Appendix 13.3 will be summarized for the overall and by 3-month interval during the Exposure Period. Subject numbers for those meeting the abnormal criteria will also be presented.

All 12-Lead ECG parameters will be listed per visit, including the change from baseline and a abnormality criteria flag. In addition, the data from patients with at least one finding will be listed with the finding.

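### Early-discontinuation ECGs mapped to a visit with no scheduled ECG drop out of the per-visit QTc classification and the investigator's clinical-significance table

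*SAP*

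**What the plan says.** SAP 3.2.3.1 deals with safety assessments made at an EDV. Where the EDV coincides with a planned visit, the rule is that "in-clinic safety assessments such as vital signs, ECGs, and blood collection for clinical laboratory assessments, should correspond to that scheduled visit". If it falls between visits, "In-clinic safety assessments at an EDV that occurs on a day between two scheduled visits will be assigned to the next scheduled clinic visit". ECGs are named as in scope. Neither sentence asks whether the assessment is due at the receiving visit.

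The following paragraph of the same section sets what the tables contain: "In the by-visit summary tables, only nominal (scheduled) visits where the assessment is scheduled will be included". EDV keeps its own label only in the listings: "In the subject listing, data will be presented under the actual visits, including EDV and unscheduled visits".

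On the ECG schedule, SAP 9.5.2 states: "The 12-Lead ECG results are collected at Entry Visit, Visit 3, Visit 5 and at visits every 6 months thereafter". Protocol 8.1.6 restricts the ECG in the three-monthly block to Visits 7, 9 and 11. Protocol Table 5-1 and SAP Table 2-1 agree and add EOS and EDV. No ECG is scheduled at Visits 2, 4, 6, 8 or 10. Protocol 8.1.7 requires an ECG at every EDV.

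SAP 9.5.2 plans four kinds of ECG summary:
- continuous parameters by scheduled visit, with Last Visit, maximum and minimum;
- QTc bands: "QTcB and QTcF will also be presented by following classification per visit";
- the investigator's overall result at each scheduled assessment visit, with subjects having an ECG result at that visit as the denominator;
- abnormal values under Appendix 13.3, overall and by 3-month interval of exposure.

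**The concern.** The two rules in SAP 3.2.3.1 work against each other. The first moves an EDV ECG to the next visit whether or not an ECG is due there. The second admits only visits where one is due. For half of the visits that follow entry and precede EOS, the ECG is moved to a place that the table does not print, so it enters neither numerator nor denominator of any visit row.

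This matters because safety is the primary objective, and Protocol 6.3 makes clinically significant ECG change and QTc thresholds grounds for withdrawal. Discontinuation can therefore depend on the ECG itself. A table of ECG findings by visit that leaves out some of the ECGs taken at discontinuation may understate those findings. The SAP was also revised because of early termination (SAP 3.9), so EDVs may be more common than the two-year design foresaw.

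**Working it through.** The documents state no figure on this point, so there is none to reproduce. The check applies the SAP 3.2.3.1 rules to the visit schedule.

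**Inputs.** Visit schedule and ECG visits: Protocol Table 5-1 and 8.1.6, SAP Table 2-1 and 9.5.2. Month length of 30 days: SAP 3.2.5. Nominal days: V1 = 1, V2 = 14, V3 = 28, V4 = 60, V5 = 90, then every 90 days to EOS = 720. Visit windows are ignored.

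**Count.** Days strictly between visits at days a and b = b − a − 1.

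| EDV falls between | Days | Receiving visit has an ECG? |
|---|---|---|
| V1 and V2 | 12 | no |
| V2 and V3 | 13 | yes |
| V3 and V4 | 31 | no |
| V4 and V5 | 29 | yes |
| V5 and V6 | 89 | no |
| V6 and V7 | 89 | yes |
| V7 and V8 | 89 | no |
| V8 and V9 | 89 | yes |
| V9 and V10 | 89 | no |
| V10 and V11 | 89 | yes |
| V11 and EOS | 89 | yes |

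- All days: 12 + 13 + 31 + 29 + 7 × 89 = 708.
- Days with no ECG row at the receiving visit: 12 + 31 + 3 × 89 = 310.
- Share: 310 / 708 = 43.8%, in 5 of 11 gaps.

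The same-day sentence has the same effect, since an EDV on the Visit 6 day maps to Visit 6. Counting whole gaps including the receiving visit's day, with entry as day 0, gives 14 + 32 + 3 × 90 = 316 of 720, or 43.9%.

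The share is higher early on. To day 180 it is (12 + 31 + 89) / (180 − 6 visit days) = 132 / 174 = 75.9%. To day 360 it is (132 + 89) / (360 − 8 visit days) = 221 / 352 = 62.8%.

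**Laboratory tests and vital signs.** Laboratory samples are due at Visit 3 and every later Evaluation Period visit, so only the gap before Visit 2 is affected: 12 / 708 = 1.7%. Vital signs are due at every visit and are unaffected.

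**What the other summaries recover.** SAP 3.2.4 defines Last Visit, minimum and maximum over all assessments up to the last dose, so an EDV ECG taken during exposure enters them. The Appendix 13.3 summaries run by exposure interval, not by visit, so the mapping does not govern them. All ECG data are listed.

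**What they do not recover.** The QTc classification has observed bands <450, 450–<480, 480–<500 and ≥500 ms, and change bands <30, 30–<60 and ≥60 ms. For subjects aged 17 or over, Appendix 13.3 flags QTc only above 500 ms or with an increase of at least 60 ms. Take an illustrative EDV ECG on day 120 with QTcF 485 ms, up 45 ms. It maps to Visit 6 and has no row in the classification. Since 485 is not above 500 and 45 is below 60, it is not flagged under Appendix 13.3 either. It remains as one value within continuous summaries and as a line in a listing. The investigator's overall result is likewise not an Appendix 13.3 criterion.

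**The case against.** The strongest reply is that little is lost. The threshold table most likely to be read for ECG safety covers marked QTc prolongation, PR, QRS and heart rate, overall and by 3-month interval, and it is untouched. The continuous tables carry Last Visit, minimum and maximum, and the listings show EDV under its own name. All of this stands, and it confines the point to two tables.

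SAP 3.2.4 also includes Last Visit in by-visit summaries unless noted otherwise. On that default the QTc classification, and perhaps the investigator's table, would gain a Last Visit row. This is possible but not settled: SAP 9.5.2 names Last Visit only for the continuous summary, and words the investigator's table by scheduled assessment visit. A Last Visit row would also pool completers with discontinuers.

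One could read the next scheduled visit as the next visit at which that assessment is due. The text does not say so, and the SAP states that very condition in its second rule when it wants it.

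A reader might infer four stronger things that the documents do not support:
- That these ECGs vanish from the analysis. They do not, as shown above.
- That 44% of discontinuing subjects are affected. The figure counts days; no distribution of discontinuation times is given.
- That most final ECGs will be EDV ECGs, or that visit rates will rest mainly on those who stayed. Early termination makes the first plausible, but no counts are given. If sponsor termination caused most EDVs, those subjects were not selected for safety problems, which weakens the bias argument.
- That Last Visit commonly misses the EDV ECG. The EDV precedes the taper, and taper drug is dispensed at it, so the ECG normally falls on or before the last dose. The exception is a subject who had already stopped.

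**Conclusion.** The point holds as a limited reporting gap. As written, SAP 3.2.3.1 removes an EDV ECG from the visit rows whenever it is mapped to Visit 2, 4, 6, 8 or 10. The practical loss is in the QTcB/QTcF classification, chiefly its intermediate bands, and in the investigator's clinical-significance table. The laboratory effect is minor. The primary safety variables, which are TEAE incidences, are not touched, and every ECG analysis here is descriptive.

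The 43.8% rests on nominal visit days, 30-day months and no visit windows, and describes calendar time only. The conclusion also rests on the literal reading of the mapping sentence and on SAP 9.5.2 not stating a Last Visit row for the two categorical tables. It is worth correcting because a stated rule drops discontinuation ECGs from two planned safety tables and the remedy is cheap.

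**What to change.** In SAP 3.2.3.1 and 9.5.2, present EDV assessments in their own EDV row in the by-visit ECG tables, including the QTc classification and the investigator's overall result, and in the laboratory tables. This replaces forward mapping to a visit where the assessment is not scheduled. State also that the two categorical ECG tables include a Last Visit row and that the QTc categories are shown for the maximum post-Baseline value.

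Mapping forward to the next visit that does have an ECG is the less good repair. A day-91 ECG would be labelled Visit 7, 270 − 91 = 179 days late, in a row for follow-up that the subject never reached. Doing that as well as adding an EDV row would show the same ECG twice.

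The cost is a short text change and a small programming change, repeated for the region outputs where these apply and for the Japan and non-Japan outputs required by SAP Section 15. No new data are needed and study conduct does not change.
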